- Any adverse event related to patient specific adherence
- Any unanticipated serious adverse device effect (USADE)

Note 1: Death, stroke, bleeding complications, and major vascular complications are adjudicated by an Independent Medical Reviewer (IMR).

6.4. *Overview of Objectives and Endpoints*

Table 6.4-1 provides an overview of the aforementioned study objectives and endpoints and a justification for the specific endpoints.

Table 6.4-1: Overview of Objectives and Endpoints

Objective	Endpoint	Rationale for Endpoint
Primary Endpoint		
Evaluate feasibility and safety of the device and the procedure	Technical success (successful delivery of the device to the correct anatomical position and successful operation and removal of the Vortex circulatory support system) and clinical success (no conversion to open heart surgery and no in-hospital mortality).	Assess the ability of the device to be delivered and removed as intended and operate as intended without in-hospital mortality or conversion to open heart surgery during HR-PCI. Mortality events are adjudicated by an IMR.

Table 6.4-1: Overview of Objectives and Endpoints

Objective	Endpoint	Rationale for Endpoint
Additional Measurements		
Evaluate safety of the device and procedure	Safety events collected through 72 hours post-procedure or hospital discharge, whichever comes first.	Evaluate safety using event definitions based on MCS-ARC recommendations ²⁸ . Mortality, stroke, bleeding complications, and major vascular complications are adjudicated by an IMR.

[figure not shown]
Abbreviations: HR-PCI=high-risk percutaneous coronary intervention; IMR=independent medical reviewer; MCS-ARC=Mechanical Circulatory Support Academic Research Consortium

7. Study Design

The Vortex Feasibility Study is a prospective, multicenter, open-label, single-arm study to assess the safety and feasibility of the Vortex System in subjects undergoing elective high-risk percutaneous coronary intervention (HR-PCI).

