d: 12-lead ECG; baseline ECG should be done within 30 days prior to the index procedure; post-procedure timing is per standard of care for HR-PCI.

e: Laboratory tests at baseline include CBC with platelets, serum creatinine, plasma-free hemoglobin, and cardiac enzymes. Post-procedure, cardiac enzymes (CK or troponin is required, CK-MB or troponin if CK is elevated) must be collected once per standard of care within 6–24 hours; if readings are abnormal, a second collection per standard of care is required. Plasma-free hemoglobin must be collected pre-discharge (≥ 6 hours post procedure). Plasma-free hemoglobin may be collected during the index procedure per the standard of care.

f: Minimum required iliofemoral diameter is > 5.5 mm; any assessment technique to determine diameter and tortuosity is permitted; assessment must be done within 365 days prior to the index procedure.

g: TTE assessment should be done within 180 days prior to the index procedure.

h: Deidentified copies of the imaging assessments should be provided to Boston Scientific.

i: Coronary angiogram should be done within 365 days prior to the index procedure per standard of care for HR-PCI.

j: Information on device deficiencies for the test device will be monitored and reported to Boston Scientific.

k: The adverse event assessment includes AE, SAE, ADE, SADE, USADE, and IMR events, which will be collected from the time of enrollment through 72 hours post-procedure or hospital discharge, whichever comes first, in all subjects. Please refer to Section 18.1 for reportable events, including a list of IMR events, and to **Table 24.2-1** for definitions of these events, which specify data required for IMR adjudication.

Abbreviations: AE=adverse event; ADE=adverse device effect; CBC=complete blood count; CCS=Canadian Cardiovascular Society; CK=creatinine kinase; CK-MB=creatinine kinase myoglobin band; ECG=electrocardiogram; HR-PCI=high risk percutaneous coronary intervention; IMR=independent medical

Table 10.1-1: Data Collection Schedule

Assessment	Baseline	Index Procedure	≤72 Hours / Discharge ^a
------------	----------	-----------------	------------------------------------

reviewer; SADE=serious adverse device effect; SAE=serious adverse event; USADE=unanticipated serious adverse device effect

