10.7.3. Intraprocedural Hemodynamic Measurements

Intraprocedural hemodynamic assessment is primarily based on TTE (or intracardiac echocardiography³³ as per standard of care) and catheter-based pulmonary artery measurements. Cardiac output (CO), pulmonary artery (PA) pressure, pulmonary capillary wedge pressure (PCWP), central venous pressure (CVP), mean arterial pressure (MAP), and right atrial pressure (RAP) should be measured before and after the pump is placed and switched on via the pulmonary artery catheter and also when the pump is switched off and

removed (post-procedure). Left ventricular pressure may be measured via the pigtail catheter.

10.8. *Post-procedure (≤ 72 Hours)/Prior to Hospital Discharge*

Within 72 hours post procedure or before discharge (whichever comes first), the following assessments must be performed.

- 12-lead ECG
- Laboratory tests
 - Cardiac enzymes (CK or troponin required, CK-MB or troponin if CK is elevated) must be collected once per standard of care within 6–24 hours post-procedure; if readings are abnormal, a second collection per standard of care is required.
 - Plasma-free hemoglobin must be collected ≥ 6 hours post procedure (before discharge)
- NYHA classification
- Anticoagulation therapy and other cardiovascular medications
- Adverse event assessment (see Section 18)
- Device deficiencies assessment

10.9. *Study Completion*

All subjects will be evaluated through 72 hours or hospital discharge, whichever comes first. A subject's participation in the study will be considered complete after 72 hours or hospital discharge (whichever comes first).

10.10. *Source Documents*

It is preferable that original source documents, when available, are maintained at the investigative center. In lieu of original source documents, certified copies are required to be maintained. A certified copy is a copy (irrespective of the type of media used) of the original record that has been verified (i.e., by a dated signature or by generation through a validated process) to have the same information, including data that describe the context, content, and structure, as the original. Source documentation includes but is not limited to those items noted in **Table 10.10-1**. Source documentation provided to the Sponsor for assessment/adjudication will be deidentified per local law and regulations.

Table 10.10-1: Source Documentation Requirements

Requirement	Disposition

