17.5. Risk Minimization Actions

Additional risks may exist. Risks can be minimized through compliance with this protocol, performing procedures in the appropriate hospital environment, adherence to subject selection criteria, close monitoring of the subject's physiologic status during research procedures and/or follow-ups and by promptly supplying BSC with all pertinent information required by this protocol.

The aforementioned risks are mitigated with the following approaches.

- Estimation of risks associated with the investigational device in accordance with ISO 14971 prior to conducting the clinical investigation
- Preclinical testing and bench testing of the Vortex System to establish safety and performance
- Selection of investigators who are experienced and skilled in interventional HR-PCI procedures supported by mechanical circulatory support devices
- Completion of training provided by the sponsor
- Clearly defining the inclusion/exclusion criteria to ensure only appropriate subjects are enrolled
- Confirmation of eligible subjects by investigators experienced in HR-PCI with MCS procedures
- Performing all procedures in accordance with the Vortex System IFU
- Ensuring that treatment of subjects is consistent with current medical practices, including adjunctive pharmacologic therapy
- On-site support by BSC representatives during the procedure
- Dynamic safety review processes, with Independent Medical Reviewer (IMR) adjudication

Anticoagulation medication (e.g., heparin) will be administered during the procedure per standard of care to reduce the risk of thrombosis, embolism, and stroke.

Cardiac enzyme, serum creatinine and plasma free hemoglobin measurements and electrocardiograms will be performed post-procedure to detect cardiac or renal injury.

Subjects will be carefully monitored during the procedure, and through 72 hours or hospital discharge, whichever comes first.

Data will be monitored as they are submitted to BSC.

In addition, BSC has implemented specific design and clinical mitigations to address observations from prior preclinical and clinical studies. Please refer to the Investigator Brochure for a detailed description of risk mitigations.

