24.2. Definitions

Terms are defined in **Table 24.2-1**.

Table 24.2-1: Definitions

Term	Definition
ACUTE KIDNEY INJURY (AKI) (AKIN System ^{29,30})	
Maximal change in serum creatinine from baseline through discharge or 72 hours post-procedure, whichever comes first.
 
 • Stage 1: Increase in serum creatinine to 150–199% (1.5–1.99 × increase compared with baseline) OR increase of ≥0.3 mg/dl (≥26.4 mmol/L), or urine output <0.5 ml/kg per hour for >6 but <12 hours • Stage 2: Increase in serum creatinine to 200–299% (2.0–2.99 × increase compared with baseline) or urine output <0.5 ml/kg per hour for >12 but <24 hours • Stage 3: Increase in serum creatinine to ≥300% (>3 × increase compared with baseline) OR serum creatinine of ≥4.0 mg/dL (≥354 mmol/L) with an acute increase of at least 0.5 mg/dL (44 mmol/L) OR urine output <0.3 ml/kg per hour for ≥24 hours or anuria for ≥12 hours 
Note: Subjects receiving renal replacement therapy are considered to meet Stage 3 criteria irrespective of other criteria.

ACUTE VESSEL OCCLUSION	The state of complete luminal obstruction with no antegrade blood flow.
ADVERSE EVENT (AE) Ref: ISO 14155	Any untoward medical occurrence, unintended disease or injury, or any untoward clinical signs (including an abnormal laboratory finding) in subjects, users or other

Table 24.2-1: Definitions

[figure not shown]
Term	Definition

Ref: MDCG 2020-10/1
	
persons, in the context of a clinical investigation, whether or not related to the investigational medical device and whether anticipated or unanticipated.
 
Note 1: This includes events related to the investigational medical device or the comparator.
 
Note 2: This definition includes events related to the procedures involved.
 
Note 3: For users or other persons, this definition is restricted to events related to the investigational medical device.
 
Note 4: This definition includes events related to management practices.
 
Note 5: This definition includes patient related events.

ADVERSE EVENT BECOME AWARE DATE
	
The become aware date for an adverse event that requires reporting per the protocol is the date that study personnel listed on the Delegation of Authority Log identify or are notified of the event.

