BLEEDING COMPLICATIONS ²⁸	
MCS-ARC Bleeding Adverse Event
 
 • Type 1: Bleeding that is not actionable and does not cause the patient to seek unscheduled performance of studies, hospitalization, or treatment by a healthcare professional; may include episodes leading to self-discontinuation of medical therapy by the patient without consulting a healthcare professional. This type is not relevant during a hospitalization. • Type 2: Any overt, actionable sign of hemorrhage (e.g., more bleeding than would be expected for a clinical circumstance, including bleeding found by imaging alone) that does not fit the criteria for Type 3, 4, or 5 but does meet at least one of the following criteria: 
 1) requiring nonsurgical medical intervention by a health care professional; 2) leading to hospitalization or increased level of care; or 3) prompting evaluation. • Type 3: 
 - Type 3a: 
 ○ Overt bleeding accompanied by hemoglobin drop of 3 to < 5 g/dl or (1.86–3.1 mmol/liter SI units) (provided hemoglobin drop is related to bleed) ○ Any transfusion with overt bleeding - Type 3b: 
 ○ Overt bleeding plus hemoglobin drop 5 g/dl (3.1 mmol/liter) or greater (provided hemoglobin drop is related to bleed). ○ Cardiac tamponade ○ Bleeding requiring surgical intervention for control (excluding dental/nasal/skin/hemorrhoid) ○ Bleeding requiring intravenous vasoactive agents

Table 24.2-1: Definitions

Term	Definition

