3.2 Additional Measurements

Safety events will be collected through 72 hours post-procedure or hospital discharge, whichever comes first, as listed below. Death, stroke, bleeding complications, and major vascular complications are adjudicated by an Independent Medical Reviewer (IMR).

- Stroke/transient ischemic attack (TIA)
- Cardiac tamponade
- Cardiac death

- Myocardial infarction (MI)
- Bleeding complications: Type 3–5 based on the Mechanical Circulatory Support Academic Research Consortium (MCS-ARC) definitions
- Acute kidney injury (AKI; based on the AKIN System Stage 3 [including renal replacement therapy] or Stage 2)
- Major vascular complications
- Any device-related adverse event (adverse device effect [ADE]/serious adverse device effect [SADE])
- Any procedure-related adverse event
- Any adverse event related to management practices
- Any adverse event related to patient specific adherence
- Any unanticipated serious adverse device effect (USADE)

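### Post-procedure serum creatinine is promised in Protocol Section 17.5 but missing from the visit schedule, so a low or zero AKI rate could reflect tests not done

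*Protocol*

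**What the plan says.** Protocol Table 10.1-1 marks laboratory tests as required at baseline and again at the 72-hour or discharge visit. Footnote e gives the content of that row. For baseline: "Laboratory tests at baseline include CBC with platelets, serum creatinine, plasma-free hemoglobin, and cardiac enzymes". For after the procedure, it names cardiac enzymes and plasma-free hemoglobin only.

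Protocol Section 10.8 opens with "Within 72 hours post procedure or before discharge (whichever comes first), the following assessments must be performed". Its laboratory entries are the same two tests. Section 10.5 lists creatinine and the complete blood count among assessments due before the index procedure.

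Protocol Section 17.5, on risk minimization, says: "Cardiac enzyme, serum creatinine and plasma free hemoglobin measurements and electrocardiograms will be performed post-procedure to detect cardiac or renal injury".

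AKI at AKIN Stage 2 or 3 is one of the additional safety measurements (Protocol Section 6.3, SAP 3.2). Protocol Table 24.2-1 defines it as "Maximal change in serum creatinine from baseline through discharge or 72 hours post-procedure, whichever comes first". The staging also allows low urine output, and for dialysis it adds that "Subjects receiving renal replacement therapy are considered to meet Stage 3 criteria irrespective of other criteria".

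SAP 3.2.1 reports a numerator, denominator and proportion. SAP 7.4.3 puts every subject of the analysis set in the denominator and treats all as having sufficient follow-up. SAP 7.3 leaves the handling of missing data to depend on how often it occurs and on the type of outcome.

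**The concern.** The test that chiefly defines a named safety outcome is absent from the two places that tell a site what to do after the procedure. A coordinator working from Table 10.1-1 and Section 10.8 could complete every listed item and never draw a post-procedure creatinine. Nothing in the SAP tables would then show the difference between a subject tested and found normal and a subject not tested.

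This matters because the study is a first-human-use study with a safety objective, AKI is a listed risk in Table 17.1-1, and Section 17.5 offers post-procedure creatinine as a risk mitigation. With at most 10 subjects, the reader of the final report will look at the AKI line as a simple count. If some of the zeros are unmeasured, that count is too reassuring.

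**Working it through.** The plan states no figure for AKI, so there is nothing to reproduce. The check is a comparison of passages, followed by one line of arithmetic.

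1. **Is creatinine required after the procedure?**
   - Section 17.5: yes, stated as something that will be done.
   - Table 10.1-1, laboratory row: required at 72 hours or discharge, but the row does not name tests.
   - Footnote e, which names them: not listed after the procedure.
   - Section 10.8, mandatory list: not listed.
   - Section 10.5: listed, but only before the procedure.

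   The general commitment and the operative lists do not match.

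2. **Can AKI be found another way?** Stage 2 or 3 can be reached by urine output or by renal replacement therapy. Urine output is in neither Table 10.1-1 nor Section 10.8. Renal replacement would be noticed, but it captures only the most severe cases. An abnormal laboratory finding is a reportable adverse event (Protocol Section 18.1 and Table 18.2-1), but only if the test was done.

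3. **Would adjudication catch a missing value?** Note 1 to Protocol Section 6.3 limits the Independent Medical Reviewer to death, stroke, bleeding complications and major vascular complications. AKI is not among them, so its count rests on what sites measure and report.

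4. **What happens in the table?** SAP 7.4.3 includes all subjects in the denominator. SAP 7.4.1 removes missing values from denominators, but only for baseline categorical variables. SAP 7.3 has specific rules for partial adverse event dates and none for a missing creatinine. An untested subject with no other qualifying event would therefore most likely add 1 to the denominator and 0 to the numerator.

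5. **How large could the effect be?** The documents do not say how many subjects would have a value, so that number is an assumption here. Let 10 be enrolled (the maximum) and m have post-procedure values sufficient to show their maximal change, with no AKI seen. The true number of cases then lies between 0 and 10 − m:
   - m = 10: 0 cases, 0%
   - m = 7: 0 to 3 cases, 0% to 30%
   - m = 5: 0 to 5 cases, 0% to 50%
   - m = 3: 0 to 7 cases, 0% to 70%

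   If untested subjects are counted as event-free, the table would print 0/10 in all four cases. Each missed case is 1/10 = 10 percentage points, and more if fewer than 10 are enrolled or in the per-protocol set. These are logical bounds, not estimates; urine output, dialysis or locally obtained values would narrow them.

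**The case against.** The strongest reply is that Section 17.5 belongs to the same binding protocol. Footnote e and Section 10.8 are silent on creatinine; they do not exclude it. The laboratory row is marked required after the procedure, and the AKI definition presupposes a value through discharge or 72 hours. A site that skipped the test would depart from Section 17.5. These subjects are in hospital after a high-risk intervention, and local practice may supply creatinine in all of them. Protocol Section 11.3 and SAP 5 summarize collected continuous variables with n, and SAP 5.6 allows subject listings, which are easy to read at this sample size.

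Part of this stands. The mismatch is better called an omission from the operative lists than a flat contradiction, and the bias may be nil. The rest does not remove the point. Section 10.8 is written as the list of what must be done and names other blood tests explicitly. A summary with n helps only if creatinine is captured as a data field, which cannot be seen because the eCRF is not in the documents. The listings are optional. The content of Figure 10.1-1, which also shows the schedule, is not visible in the text available for review.

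A reader might also infer a second, parallel fault for bleeding, since no post-procedure blood count is scheduled and Type 3a includes "Overt bleeding accompanied by hemoglobin drop of 3 to < 5 g/dl". The documents do not support putting that on the same footing. No passage promises a post-procedure blood count, so nothing conflicts. The hemoglobin criteria of Types 3a and 3b apply only with overt bleeding, and Type 3 can also be met by transfusion, tamponade, surgical control or vasoactive agents. Types 4 and 5 have further routes, and bleeding is adjudicated. At most this is a minor optional note about an overt bleed that meets no other criterion and has no hemoglobin value.

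**Conclusion.** The omission is confirmed in the text and should be fixed. Section 17.5 commits to a post-procedure creatinine that footnote e and Section 10.8 do not carry, while a named safety rate depends mainly on that test. The consequence is a possible downward bias in the AKI rate. Its size cannot be derived from the documents: it is nil if every site tests routinely, and 10 percentage points for each missed case among 10 subjects.

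Two stronger readings are tempting and go too far. One is that the SAP instructs that untested subjects be counted as free of AKI. It does not: SAP 7.4.3 fixes the denominator, while SAP 7.3 leaves missing data open, so that result is likely but is not a stated rule. The other is that AKI will go unmeasured in some definite share of subjects. The documents give no such share, and the values of m used above are assumptions.

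The measurement is descriptive, with no hypothesis or threshold attached, and the primary endpoint does not depend on it.

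**What to change.** **Protocol.** Reconcile Table 10.1-1 footnote e and Section 10.8 with Section 17.5 on post-procedure serum creatinine, with the timing set by the sponsor. Because the definition uses the maximal change, the sponsor should decide whether one value is enough. If the eCRF does not already do so, creatinine values obtained clinically through 72 hours or discharge should be recorded.

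**SAP.** In SAP 3.2.1, report the number of subjects with a post-procedure creatinine beside the AKI numerator, denominator and proportion. No interval or test is needed.

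**Cost.** The protocol change touches one footnote and one list, but under Section 15.3 it needs ethics committee and Swedish Medical Products Agency approval before use. It adds local blood tests that Section 17.5 already promises, possibly more than one draw each, in at most 10 subjects, with a small data-entry load. The SAP change is one added count and can be made before database lock under SAP 5.7 without a protocol amendment. If the protocol is being amended anyway, the sponsor may consider whether to schedule a post-procedure hemoglobin too; that is optional.

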10.2. Study Candidate Screening

Subjects will be evaluated for eligibility by the center's heart team.

10.3. Informed Consent

Before any study specific tests or procedures are performed, subjects who meet eligibility criteria will be asked to sign the study Informed Consent Form (ICF) that was approved by the Independent Ethics Committee (IEC)/Human Research Ethics Committee (HREC). Subjects must be given ample time to review the ICF and have questions answered before signing.

Study personnel should explain to the subject that even if the subject agrees to participate in the study and signs the ICF, screening tests and procedures may demonstrate that the subject is not a suitable candidate for the study.

10.4. Screening Assessments

The screening tests and procedures listed below must be performed to confirm a subject's eligibility for the study. Specific data points will be collected in the electronic Case Report Forms (eCRFs) as shown below.

- Clinical assessments
 - Demographics including age and gender
 - Medical history, including cardiac, neurological, renal disease, peripheral disease and other medical conditions
 - Physical assessment, including weight, height, and vital signs
 - New York Heart Association (NYHA) classification
 - Canadian Cardiovascular Society (CCS) angina classification
 - 12-lead electrocardiogram (ECG; see *Note 1* below)
 - Current anticoagulant and other cardiovascular medications
- Imaging assessments (see *Note 1* and *Note 2* below)
 - Transthoracic echocardiography (TTE)
 - Coronary angiogram

- Evaluation of iliofemoral diameter and tortuosity (any assessment technique is permitted)

Note 1: Baseline ECG should be done within 30 days prior to the index procedure, TTE within 180 days prior to the index procedure, coronary angiogram per standard of care for HR-PCI, and iliofemoral diameter/tortuosity assessment within 365 days prior to the index procedure.

Note 2: Imaging assessments should include basic cardiac measurements, including ventricular dimensions, function of the left and right ventricle, and function of all cardiac valves. Deidentified copies of the imaging assessments should be provided to Boston Scientific.

